10.3 Ethical Conduct of the Study

The procedures set out in this protocol pertaining to the conduct, evaluation, and documentation of this study are designed to ensure that the sponsor and investigator follow Good Clinical Practice (GCP) Guidelines and the guiding principles detailed in the Declaration of Helsinki. The study will also be carried out in keeping with applicable local laws and regulations. An inspection by the sponsor representatives and/or their designee and/or healthy authority or other authorized regulatory authorities representatives may occur at any time. The investigator must agree to the inspection of study-related records by the regulatory authority/sponsor representatives, and must allow direct access to source documents to the regulatory authority/sponsor representatives.

The investigator is responsible for complying with the protocol and all appropriate regulations and guidelines governing global clinical research. Additionally, he/she is responsible for ensuring that all participating staff members are adequately trained and competent to perform his/her assigned tasks.

Modifications to the study protocol will not be implemented by either the sponsor or the investigator without agreement by both parties. However, the investigator may implement a deviation from or a change of the protocol to eliminate any immediate hazards to the trial subjects without prior IRB or sponsor approval/favorable opinion. As soon as possible, the implemented deviation or change, the reasons for it, and if appropriate, the proposed protocol amendment should be submitted to the head of the investigational site, IRB (via the head of the investigational site)/sponsor.

Any deviations from the protocol must be fully explained and documented by the investigator. The circumstances, action taken, and impact of the deviation on the trial must be communicated by the principal investigator to the designated medical monitor. Any subsequent actions will be assessed by the designated medical monitor and documented.

10.4 Subject Information and Consent

The investigator will draft the informed consent form based on the protocol. The sponsor will review the investigator's draft informed consent form prior to submission to the IRB and the final IRB approved document must be provided to the sponsor for regulatory purposes.

Prior to the beginning of the study, the investigator must have received from the IRB the written approval or favorable opinion of the informed consent form and any other written information to be provided to subjects. The written approval of the IRB together with the approved subject information and informed consent forms must be filed. The informed consent form must contain all elements required by the Federal Drug Administration under 21 Code of Federal Regulations Part 50 and the ICH GCP Guidelines (E6) in addition to any other elements required by regulations or institutional policy.

Written informed consent must be obtained before any study-specific procedure takes place. Participation in the study and date of informed consent given by the subject should be documented appropriately in the subject's files. A copy of the signed informed consent form must be provided to the subject. If applicable, it will be provided in a certified translation in the language understood by the subject, if not English. Signed consent forms must remain in each subject's study file and must be available for verification by study monitors at any time.

10.5 Subject Confidentiality

The information obtained during the conduct of this clinical study is confidential, and disclosure to third parties other than those noted below is prohibited. Information obtained during the conduct of this study will be used by the sponsor in connection with the development of the investigational product. The study investigator is obliged to provide the sponsor with complete test results and all data developed in this study. Subject-specific information may be provided to other appropriate medical personnel only with the subject's permission. To ensure compliance with current ICH guidelines, data generated by this study must be available for inspection upon request by representatives of national and local health authorities, the sponsor, and the IRB for each study site.

Subject names and other identifiers, such as photographs, audio, or videotapes, may not be disclosed in any publication without prior written authorization from the subject.

10.6 Study Monitoring

An authorized sponsor representative will conduct site visits to inspect study data, subjects' medical records, and CRFs in accordance with ICH guidelines, GCPs, and the respective national and local government regulations and guidelines.

The investigator will permit authorized representatives of the sponsor and the respective national or local health authorities, other authorized regulatory authorities, and IRB to inspect facilities and records relevant to this study.

10.7 Case Report Forms and Study Records

For each subject consented, a CRF, in paper or electronic format, will be supplied and maintained by the contract research organization (CRO) staff and signed by the investigator or authorized designee to indicate that he/she has reviewed and agrees with the entered data. This also applies to those subjects who fail to complete the trial. The reason a subject is withdrawn must be recorded in the case report form.

Entries made in the CRF must be verifiable against source documents. Source documents are defined as all medical records, medical notes, laboratory results, ECG traces and any additional document other than the CRF that has original subject information contained within it.

All CRFs and source documents should be completed following GCPs and the CRO's standard operating procedures.

10.8 Protocol Violations/Deviations

It is important to conduct the study according to the protocol. Protocol deviations will not be prospectively granted by the sponsor. If deviations occur, such as a visit or sampling window being missed, the investigator must decide whether to proceed, for example, whether or not to complete the visit or sample collection outside of the protocol-defined window. The sponsor's medical monitor must be notified immediately when protocol deviations are discovered so that a decision about whether to keep the subject in the study can be made.

Only when an emergency occurs that requires a departure from the protocol for an individual subject will there be such a departure without the sponsor's pre-approval. The nature and reasons for the protocol deviation will be recorded in the subject's CRF, and the principal investigator must notify the Sponsor.

Protocol violations must be reported in the final study report.

10.9 Access to Source Documentation

Authorized sponsor representatives will conduct site visits to inspect study data, subjects' medical records, and CRFs in accordance with ICH guidelines, GCPs, and the respective local and national government regulations and guidelines.

The investigator will permit authorized representatives of the sponsor and the respective national or local health authorities, other authorized regulatory authorities, and IRB to inspect facilities and records relevant to this study.

The center will be visited at regular intervals by a monitor to ensure compliance with the study protocol, GCP, and legal aspects. This will include on-site checking of the CRFs for completeness and clarity, cross-checking with source documents, and clarification of administrative matters.

All CRF data will be entered into a clinical database. Following the correction of any errors, the clinical database will be locked.

10.10 Retention of Data

The study file and all source data should be retained until notification is given by the sponsor for destruction.

If the investigator withdraws from the trial and relinquishes his/her responsibility for the maintenance and retention of records, he/she must notify the sponsor in writing so that arrangements can be made to properly store the trial materials.

10.11 Publication and Disclosure Policy

All data and results and all intellectual property rights in the data and results derived from the study will be the property of the sponsor, who may utilize the data in various ways, such as for submission to government regulatory authorities or disclosure to other investigators.

No publication or disclosure of study results will be permitted except as specified in a separate, written agreement between Theracos Sub, LLC and the investigator. If results of this study are reported in medical journals or at meetings, all subjects' identities will remain confidential.

Appendix 1 Schedule of Events

Study activity	Screening		In-Clinic				Follow-up
	D -28 to -1	D0	D1 predose	D1 postdose	D2	D3	D15±1d
Medical history and ICF	X						
Screening for I/E criteria	X	X					
Physical exam ¹	X	X	X				X
Demographics	X						
Admission and discharge		X				X	X
Vital signs ²	X		X	X	X	X	X
ECG ³	X		X	X		X	X
Urinalysis ⁴	X	X	X			X	X
Blood draw for clinical lab tests ⁵	X	X	X			X	X
Blood sample for PK ⁶			X	X	X	X	
Urine collection ⁷		X	X	X	X	X	
Urine pregnancy test (Female only)	X	X					X
Adverse event and concomitant medication		X	X	X	X	X	X
Study completion ⁸							X

1. Weight and height will be recorded as part of the physical examination. Height will be recorded once at screening only. A complete physical exam (PE) will be performed at screening and on clinical admission (D0). A partial PE will be performed on day 1 and at follow up visit
2. Vital signs include pulse, body temperature, respiratory rate, systolic and diastolic blood pressure. Vital signs will be determined at predose and at 4 h, 24 h (day 2) and 48 h (day 3) postdose and at the follow up visit.
3. 12-lead ECG will be conducted after 5 min resting. ECG data will be recorded at screening, on day 1 at predose and at 4 h postdose and day 3, and at follow up visit on day 15 and when clinically indicated.
4. Clean sample to be collected at each visit. If urine dipstick is positive for protein, leukocyte esterase, blood or nitrites, a microscopic examination will be performed. If the microscopic exam is suggestive, a culture may be performed at the investigators discretion. Urine drug screen will be performed at screening visit and clinic admission (D0). Alcohol (via urine or breath) will be tested at clinic admission (D0) only.
5. Blood sample at the designated visits for clinical chemistry and hematology parameters are listed in [Table 1](#). Infectious disease testing will be conducted at screening only.
6. Plasma samples for PK profile of bexagliflozin will be collected at predose and at 0.5, 1, 2, 3, 4, 5, 6, 8, 10, 12, 16, 24, 36, and 48 h postdose.
7. Urine for PD will be collected at predose (h -12 to 0), and at postdose at 0–12, 12–24, 24–36, and 36–48 h.
8. If early withdrawal occurs, activities scheduled for follow up visit should be conducted. Reasons for all withdrawals should be recorded on the CRF.

Appendix 2 The Child-Pugh Classification

Finding	Points Scored for Each Observed Finding		
	1	2	3
Encephalopathy ¹	None	1 or 2 (or suppressed with medication)	3 or 4 (or refractory)
Ascites ²	Absent	Slight or Subject on 1 medication to control ascites	Moderate or Severe or Subject on 2 medications to control ascites
Bilirubin (mg dL ⁻¹)	<2	2 to 3	>3
Albumin (g dL ⁻¹)	>3.5	2.8 to 3.5	<2.8
INR	<1.7	1.7 to 2.3	>2.3

- ¹ Grade 0: normal consciousness, personality, neurological examination, electroencephalogram
 Grade 1: restless, sleep disturbed, irritable/agitated, tremor, impaired handwriting, 5 cycles per second waves
 Grade 2: lethargic, time-disoriented, inappropriate, asterixis, ataxia, slow triphasic waves
 Grade 3: somnolent, stuporous, place-disoriented, hyperactive reflexes, rigidity, slower waves
 Grade 4: unarousable coma, no personality/behavior, decerebrate, slow 2-3 cycles per second delta activity

- ² Ascites is graded according to the following criteria:
 Absent: No ascites detectable by manual investigation.
 Slight: Ascites palpation doubtful
 Moderate: Ascites detectable by palpation
 Severe: Necessity of paracentesis, does not respond to medication treatment.

Total Score	Group	Severity
5-6	A	Mild
7-9	B	Moderate
10-15	C	Severe

[figure not shown]

AUC_{0-t}	area under the plasma concentration-time curve from the time of dosing (Time 0) to Time t
$AUC_{u(0-t)}$	area under the unbound plasma concentration-time curve from time 0 to time t
BLOQ	below the limit of quantitation
BMI	body mass index
BUN	blood urea nitrogen
Ca	calcium
CI	confidence interval
Cl	chloride
C_{last}	concentration corresponding to T_{last}
CL/F	apparent oral clearance
CL_u/F	apparent clearance relative to unbound drug concentration
cm	centimeter

GLOSSARY OF ABBREVIATIONS

C_{max}	maximum observed plasma concentration
C_{maxu}	maximum unbound plasma concentration
cps	cycles per second
CRF	case report form
CV	coefficient of variation
DBP	diastolic blood pressure
dL	deciliter
DM	data management
ECG	electrocardiogram
f_u	Unbound fraction, calculated as (free drug concentration)/(total drug concentration)
hr	hour(s)
HbsAg	hepatitis B surface antigen
Hct	hematocrit
HCV	hepatitis C virus
HDL-C	high density lipoprotein cholesterol
Hgb	hemoglobin
HIV	human immunodeficiency virus
ICF	informed consent form
INR	international normalized ration
IRAE	immediately reportable adverse event
K	potassium
kg	kilogram
KR	Kenward-Roger
L	liter
λ_z	terminal elimination phase rate constant

GLOSSARY OF ABBREVIATIONS

LC-MS/MS	liquid chromatography/mass spectrometry
LDL-C	low density lipoprotein cholesterol
LLN	lower limit of normal
LS	least square
max	maximum
MCH	mean corpuscular hemoglobin
MCHC	mean corpuscular hemoglobin concentration
MCV	mean corpuscular volume
MDMA	methylenedioxymethamphetamine
MedDRA	Medical Dictionary for Regulatory Activities
mg	milligram
min	minute
mL	milliliter
msec	millisecond
Na	sodium
NCA	non compartmental analysis
NTR	not treatment related, includes unrelated
nUGE	creatinine normalized UGE
OTC	over the counter
PCP	phencyclidine
PCS	potentially clinically significant
PD	pharmacodynamic
PE	physical examination
PK	pharmacokinetic
PR	The period that extends from the beginning of the P wave (the onset of atrial depolarization) until the beginning of the QRS complex (the onset of ventricular depolarization).

GLOSSARY OF ABBREVIATIONS

PT	preferred term
QA	quality assurance
QC	quality control
QRS	The combination of three of the graphical deflections seen on a typical electrocardiogram.
QT	Time from electrocardiogram Q wave to the end of the T wave corresponding to the electrical system
QTcB	QT corrected using Bazetts formula [$QT/(RR^{1/2})$]
RBC	red blood cell (count)
REML	restricted maximum likelihood
RR interval	intra-beat interval
SAE	serious adverse event
SAP	statistical analysis plan
SAS	statistical analysis software
SBP	systolic blood pressure
SD	standard deviation
SOC	system organ class
SOP	standard operating procedure
$T_{1/2}$	apparent terminal elimination half-life
TC	total cholesterol
TCA	tricyclic antidepressant
TEAE	treatment emergent adverse event
TG	triglycerides
T_{last}	time of last measurable (positive) concentration
TLF	table, listing, figure
T_{max}	time of maximum observed plasma concentration
TR	Treatment related - includes definitely, probably, possibly, and not likely related

GLOSSARY OF ABBREVIATIONS

T-wave	repolarization of the ventricles
UGE	urinary glucose excretion
ULN	upper limit of normal (value)
VS	vital sign
V_z/F	apparent volume of distribution
WBC	white blood cell (count)
WHO-DD	World Health Organization Drug Dictionary

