Clinical Laboratory Changes: It is the investigator's responsibility to review the results of all laboratory tests as they become available. For each abnormal laboratory test result, the investigator needs to ascertain if this is a clinically significant change from baseline for that individual subject. This determination, however, does not necessarily need to be made the first time an abnormal value is observed. The investigator may repeat the laboratory test or request additional tests to verify the results of the original laboratory tests. If this laboratory value is determined to be a clinically significant change from baseline for that subject, this is considered an AE.

Hypoglycemia will be defined as any fasting plasma glucose (FPG) value ≤ 70 mg dL⁻¹ and documented as described in [Section 6.7.3.4](#).

Any clinical significant increase in hepatic enzymes and specifically ALT or AST $>$ or $= 3x$ ULN (for healthy control subjects), or AST or ALT $>$ or $=$ to $3x$ the subject's baseline values, whichever is greater will be considered a clinical laboratory adverse event.

An increase in creatinine from baseline by 0.5 mg dL⁻¹ or more will be reported as a laboratory adverse event.

Severity: Adverse events will be graded on a 3-point scale and reported as indicated on the CRF. The intensity of an adverse experience is defined as follows:

1 = Mild: discomfort noticed, but no disruption to daily activity

2 = Moderate: discomfort sufficient to reduce or affect normal daily activity

3 = Severe: inability to work or perform normal daily activity

Investigational Product Causality: The site and database should ask for the causality relative to the study compound. Relationship of an adverse event to dosing will be assessed as follows:

Definite: There is a reasonable causal relationship between the investigational product and the AE when the event responds to withdrawal of the investigational product (dechallenge), and recurs with administration of the investigational product (rechallenge).

Probable: There is a reasonable causal relationship between the investigational product and the AE. The event responds to dechallenge. Rechallenge is not required.

Possible: There is a reasonable causal relationship between the investigational product and the AE. Dechallenge is lacking or unclear.

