Not Likely: There is a temporal relationship to investigational product administration, but there is not a reasonable causal relationship between the investigational product and the event.

Unrelated: There is no temporal or causal relationship to investigational product administration.

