9.7.1 Adverse Events

Adverse events will be mapped to preferred term (PT) and system organ class (SOC) using the Medical Dictionary for Regulatory Activities (MedDRA). The number and percentage of subjects reporting adverse events will be determined by relationship to treatment and by severity of the event. Causality for AEs will be ascribed by the investigator according to the investigational product causality guidelines of section 6.7.

Adverse event listings will be provided for the following subsets:

- all treatment emergent AEs (TEAEs).
- all TEAEs at least possibly related to bexagliflozin
- serious TEAEs (if any).
- TEAEs leading to withdrawal (if any).

AEs are dosing emergent if they occur on or after bexagliflozin administration. Causality for TEAEs will be ascribed by the investigator according to the investigational product causality guidelines of section 6.7. Only TEAEs will be tabulated in summary tables.

Tabulations will display TEAEs by severity and relationship to bexagliflozin.

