6.3.3.6 Relationship to the Investigational Medicinal Product

The relationship of an AE to dosing will be assessed as “Definite”, “Probable”, “Possible”, “Not Likely”, or Unrelated using the criteria specified in Section 6.7 of the study protocol.

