8.4.1 Adverse Events

All AEs will be coded to system organ class (SOC), and preferred term (PT), using the latest Medical Dictionary for Regulatory Activities coding dictionary (version to be specified in the clinical study report). All reported AEs will be listed, but only TEAEs will be summarized.

The incidence of all TEAEs will be summarized by hepatic function group. In the summary tables, subjects may be counted under multiple SOCs and PTs, but for each SOC and PT, subjects are only counted once. If a subject has the same AE on multiple occasions, the highest severity (severe > moderate > mild) or drug relationship (definite > probable > possible > not likely related > unrelated) recorded for the event will be presented. If severity is missing, subjects will be included as missing (for severity). If drug relationship is missing, subjects will be included in related tables (e.g., considered treatment related [TR]). Summary tables will be organized by SOC, then PT.

The following summaries will be presented for TEAEs for each hepatic function group and for all subjects for selective summaries for the Safety Population.

- Overall Summary of TEAEs by hepatic function group
- Incidence of TEAEs by hepatic function group, system organ class, and preferred term
- Incidence of Treatment Emergent Serious Adverse Events by hepatic function group, system organ class, and preferred term

Subjects who prematurely withdraw due to TEAEs and subjects with serious TEAEs will be listed for the Safety Population.

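### The SAP glossary classes Not Likely adverse events as treatment related, against the protocol's causality criteria and its cut-off at Possible

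*SAP*

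**What the plan says.** The SAP's Glossary of Abbreviations is the only place that splits causality into two groups. TR is "Treatment related - includes definitely, probably, possibly, and not likely related". NTR is "not treatment related, includes unrelated".

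SAP 6.3.3.6 lists five levels (Definite, Probable, Possible, Not Likely, Unrelated) and takes their meaning from the protocol: "or Unrelated using the criteria specified in Section 6.7 of the study protocol".

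Protocol 6.7 defines those levels. The lowest that asserts causation reads "Possible: There is a reasonable causal relationship between the investigational product and the AE". Not Likely has a temporal relationship, "but there is not a reasonable causal relationship between the investigational product and the event". Unrelated has neither a temporal nor a causal relationship.

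Protocol 9.7.1 asks for a listing of "all TEAEs at least possibly related to bexagliflozin".

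SAP 8.4.1 mentions TR once, in the rule for a missing relationship: "subjects will be included in related tables (e.g., considered treatment related [TR"]). For repeated events it says the highest "drug relationship (definite > probable > possible > not likely related > unrelated) recorded for the event will be presented". That ranks the levels but draws no line between related and not related.

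**The concern.** The investigator rates causality by the protocol 6.7 criteria, and the SAP then groups the ratings. The grouping should respect what the ratings mean. Under the glossary, an event for which the investigator has recorded that no reasonable causal relationship exists becomes treatment related.

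Safety and tolerability in moderate hepatic impairment is the secondary objective (protocol 2.2, SAP 2.2), and a count of related TEAEs by hepatic function group is a natural summary for it. If that count is built on TR, it will disagree with the protocol's own related listing whenever a subject's most-related rating for an event is Not Likely. A reader of the study report would then see two different sets of related events with no explanation.

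The category could matter in practice. A TEAE occurs on or after dosing by definition, so a coincidental event during the 48 h confinement may well be seen as temporally related and rated Not Likely rather than Unrelated. The protocol does not define a temporal relationship, so how often this would happen cannot be said.

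**Working it through.** The documents give no figure to reproduce. The check is to map each of the five levels to related or not related under each source and compare.

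| Level | Protocol 6.7: reasonable causal relationship | Protocol 9.7.1: in the related listing | SAP glossary |
|---|---|---|---|
| Definite | yes | yes | TR |
| Probable | yes | yes | TR |
| Possible | yes | yes | TR |
| Not Likely | no | no | **TR** |
| Unrelated | no | no | NTR |
| Related levels | 3 of 5 | 3 of 5 | 4 of 5 |

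1. The two protocol sections agree with each other: 3 related levels and 2 not related.
2. The SAP glossary has 4 related levels and 1 not related. The difference is 4 − 3 = 1 level, Not Likely.
3. Is the difference declared? SAP Section 1 requires a sound statistical rationale for deviations. SAP Section 10, on changes from the protocol's methods, mentions no change to the relatedness cut-off. No other section reconciles the definitions.
4. Would the definition be used? SAP 8.4.1 refers to related tables and gives TR as their label. Since 8.4.1 supplies only a ranking, a programmer needing a cut-off would take it from the glossary.
5. How does it interact with the counting rules? SAP 6.3.3.4 (rule 4) keeps the most-related rating when the same preferred term recurs. A subject with one event rated Not Likely and a repeat rated Unrelated is therefore carried at Not Likely, and the glossary then makes that subject related. This follows from the TR definition and is not a separate error.
6. Scale only: with eight subjects planned per group, one reclassified subject changes a group's incidence by 1/8 = 12.5 percentage points. This is not a forecast, because neither document gives an expected number of Not Likely events.

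**The case against.** The strongest reply is that no output is shown to depend on the definition. In the body of the SAP, TR appears once, as an example within the missing-relationship rule, and NTR appears only in the glossary. None of the three TEAE summaries bulleted in SAP 8.4.1 is a table of related events. The shells are in a companion document (SAP Section 1 and Appendix 4) and may show all five levels. This stands as a limit on the consequence, but it does not rescue the definition. If the shells use the protocol's cut-off, they contradict the SAP; if they use TR, the outputs contradict the protocol.

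Second, protocol 6.7 never uses the term treatment related and sets no two-way split, and the cut-off in protocol 9.7.1 is stated for a listing. The protocol's tabulations by relationship specify no grouping. Because protocol 6.7 separates Not Likely from Unrelated by the temporal link, a deliberately wide grouping at that boundary would be coherent. Each of these statements is correct. Even so, 9.7.1 contains the only relatedness cut-off in the protocol, it falls exactly where the 6.7 wording changes from a reasonable causal relationship to none, and the SAP does not say that a wider grouping was intended.

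Third, the harm is small. All AEs are listed, no hypothesis is tested (SAP 3.3), the highest relationship for repeated events is to be presented, and the error attributes too much to the drug rather than too little. This stands too, and it is why the point concerns safety reporting only. It does not make it acceptable to label as drug related an event the investigator judged otherwise.

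**Conclusion.** The concern holds. The TR and NTR entries are wrong as written: they place Not Likely in the related group, against the criteria the SAP itself adopts and the protocol's cut-off at Possible, and the departure is not declared.

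The size is one of five causality levels. The effect on any incidence is unknown. It depends on two things the documents do not show: how many subjects have Not Likely as their most-related rating for an event, and which outputs group by TR. Confidence is high on the mismatch in wording; the effect on reported tables is conditional on the unseen shells.

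The consequence is limited to descriptive safety reporting and does not touch the primary PK and PD analyses. No event would be hidden. It should be corrected before database lock.

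**What to change.** Change the two SAP glossary entries so that TR means definite, probable or possible, and NTR means not likely or unrelated. Then check the table and listing shells against the new definition.

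Keep the SAP 8.4.1 rule that a missing relationship counts as TR, and add one sentence calling it a conservative convention. Showing such subjects on their own line would keep them distinct from events actually rated Possible or above, but this is optional.

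As a minor consistency step, the bullets in SAP 8.4.1 could name the severity and relationship tabulations that its text already presupposes, together with the related listing from protocol 9.7.1.

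If the sponsor does want Not Likely counted as related, the alternative is to declare and justify that in SAP Section 10 and to label the affected outputs so that they are not confused with the protocol's listing.

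The cost is two glossary edits, one sentence, up to three named outputs and a check of the shells. All of it is in the SAP and its shells; no protocol amendment or new data is needed.
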